Efficacy Study of the LARA Wheelchair System for Subacute Stroke Patients

NCT 02830893

Standard Operating Procedures

February 28, 2018

Table of Content

- 1. Background and Population
- 2. Inclusion and Exclusion Criteria
- 3. Methods
- 4. Timeline of the Study
- 5. Table of Clinical Testing
- 6. List of Clinical Tests
- 7. Daily Study Procedures
- 8. Statistical Considerations

Background

We will recruit 44 individuals with an acute or subacute stroke (3 days to 30 days post stroke) to participate in this randomized controlled trial at UCI ARU and Rancho Los Amigos National Rehabilitation Center. These individuals will have an acute or subacute stroke with arm/ hand weakness defined as a score of less than 50 (out of 66) on the arm motor scale of the Fugl-Meyer Assessment.

Inclusion Criteria:

- 1. History of stroke affecting the arm, at least 3 days to 30 days prior to enrollment
- 2. Age 18 to 80 years of age
- 3. Upper extremity weakness, defined as a score of less than 50 (out of 66) on the arm motor scale of the Fugl-Meyer Assessment

Exclusion Criteria:

- 1. Moderate to severe pain in the stroke-affected upper extremity (score >6 on 10-point visual analog pain scale), at rest or increased when attempting to use LARA
- 2. Severe tone at the affected upper extremity (score >4 on the Ashworth Spasticity Scale)
- 3. Severe aphasia (score of 2 or higher on the NIH stroke scale question 9)
- 4. Deficits in vision, language, attention, or other cognitive functions severe enough to interfere with using LARA
- 5. Currently pregnant
- 6. Difficulty in understanding or complying with instructions given by the experimenter
- 7. Inability to perform the experimental task that will be studied

Methods:

The primary outcome measure will be the Upper Extremity Fugl-Meyer Score to assess motor impairment in the affected arm. Secondary outcome measures will be Box and Blocks Test, Modified Ashworth Scale of Spasticity to measure spasticity of the shoulder, elbow, wrist and hand, Visual Analog Pain scale to assess pain, NIH Stroke Scale, mini mental state exam to assess cognitive function and the Borg scale to access their perceived exertion levels. We will perform testing at three separate evaluations: At the initial baseline visit, 3-weeks post therapy or the day before discharge if sooner, and 3-month follow up. The end point of the study will be the 3-month after baseline evaluation.

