After the baseline evaluation, all participants will be randomized into 2 groups: LARA group versus conventional hand and arm exercise program. Randomization will be done through a web-based program.

For LARA group: participants will be fitted for a LARA chair, they will receive a demonstration by a research therapist and be instructed on how to get in/out of the LARA chair, how to propel LARA in a straight line, turns, figure 8 if possible. Participants will also receive training on how to perform arm exercises using a video gaming program. Participants will receive 2 sessions lasting 30 mins each for these training exercises. Participants will begin his/her exercise routine starting the third session. A research therapist will be available to assist but study participants are expected to perform exercise routines by themselves as much as possible. The research therapist will record and keep a log of time spent assisting study participants every day.

If supervising therapists believe LARA participants are skilled enough to drive LARA, participants will begin using LARA to go to therapy appointments and move around ARU by themselves throughout the study.

For control group: participants will receive a demonstration by a research therapist and instructions on how to perform arm/hand exercise programs using towel and table. Towels, tables and an exercise log will be provided. Participants will receive 2 sessions lasting 30 minutes for each training. Participants will begin his/her exercise routine starting the third session. A research therapist will be available to assist but study participants are expected to perform exercise routines by themselves as much as possible. The research therapist will record and keep a log of time spent assisting study participants every day.

Study participants will be compensated with a cash stipend of \$100 for each evaluation. Study participants will receive a maximum total of \$300 from the study.

Time Line of the Study

Visit	Week	Evaluation	Evaluation	Exercise	Training Content
# 1	1	Session #	content	session #	(order to be randomized)
	1	1	Screen		
2	1	T T	All clinical outcomes		
3	1			1	A: LARA or B: Tabletop exercise program
4	1			2	A: LARA or B: Tabletop exercise program
5	1			3	A: LARA or B: Tabletop exercise program
6	1			4	A: LARA or B: Tabletop exercise program
7	1			5	A: LARA or B: Tabletop exercise program
8	2			6	A: LARA or B: Tabletop exercise program
9	2			7	A: LARA or B: Tabletop exercise program

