- 9. If supervising therapists at ARU and research therapist believe LARA participants are skilled enough to drive LARA, participants will begin using LARA to go to therapy appointments and move around ARU by themselves.
- 10. 3 clinical evaluations: baseline, 3-week post therapy or the day before discharge if sooner, 3-month follow up. All clinical evaluations must be completed within 2 days of scheduled dates.
- 11. 3-month follow up is 3 months after baseline evaluation.

Statistical Considerations

Data will be analyzed using modified intention-to-treat analysis. That is, all participants will be included in the analysis if data from the last follow-up assessment is available, regardless of treatment they receive or deviations from protocol. For missing data, we will carry forward the last available value. The effect of treatment on each outcome measure will be assessed using a repeated-measures ANOVA. Follow up analysis will be done using t-tests with Bonferroni corrections, or Wilcoxon rank sum tests if the distributions fail the Lilliefors test for normality. We hypothesize that the participants in the LARA therapy group will have significantly greater reductions in motor impairment measured by FM score than participants in the conventional therapy group. We expect this will be due to the increased dose of therapy LARA provides, and we will include total arm activity (as measured by the wrist-mounted actigraphy) and baseline function as covariates in the analysis. We will compare changes in MAL score, ARAT score, range of motion at the shoulder and elbow, Visual Analog Pain scores, Ashworth Spasticity, and 10 min walk scores using student's t-test or Wilcoxon rank sum tests for non-parametric data. We expect improvements in functional use of the impaired limb (MAL and ARAT) and range of motion but expect no significant differences in pain, spasticity, wheelchair odometer reading, or walking speed. All analyses will be reviewed by our statistical consultant.

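### The plan expects no significant difference in pain and spasticity, but a non-significant test would meet that expectation without showing that LARA does not raise them

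*Combined protocol and SAP*

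**What the plan says.** The Methods section lists the Modified Ashworth Scale and the Visual Analog Pain scale among the secondary outcome measures. The Table of Clinical Testing schedules both at screening and at all three evaluations.

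The Statistical Considerations section covers their analysis in three places:

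- A repeated-measures ANOVA is planned for every outcome measure. It is followed by this sentence: "Follow up analysis will be done using t-tests with Bonferroni corrections", with a Wilcoxon rank sum test where normality fails.
- Change scores for a list of outcomes that includes pain and Ashworth spasticity are to be compared "using student's t-test or Wilcoxon rank sum tests for non-parametric data". No correction is mentioned there.
- For pain and spasticity, together with odometer reading and walking speed, the authors "expect no significant differences in pain, spasticity, wheelchair odometer reading, or walking speed".

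The section gives no equivalence or non-inferiority margin, no confidence-interval criterion, no significance level and no power statement. On size, the Background says: "We will recruit 44 individuals with an acute or subacute stroke". The Methods section adds that "all participants will be randomized into 2 groups: LARA group versus conventional hand and arm exercise program", without an allocation ratio.

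**The concern.** The prediction is worded in terms of significance, so a p-value above the threshold is enough to meet it. Such a p-value means only that the test failed to reject. It does not show that the arms are alike, and the smaller the analysed sample, the more easily the prediction is met whatever the truth.

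This matters more for pain and tone than for the other outcomes in that sentence. The first exclusion criterion already allows for arm pain that gets worse when LARA is attempted, and the second concerns severe tone. The Statistical Considerations section expects LARA to work by delivering more arm therapy, so readers will want to know whether the extra use raised pain or tone. If the report says only that no significant difference was found, as expected, they may conclude that it did not, when the data could be compatible with a moderate rise.

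**Working it through.** The plan offers no power or precision figure to reproduce, so this check asks what a difference test of this size can and cannot exclude.

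**Inputs from the document**
- Total sample 44 (Background); two arms (Methods).
- Pain scale: "score >6 on 10-point visual analog pain scale" (exclusion criterion 1). No SD and no clinically important difference are given.
- Analysis set: "all participants will be included in the analysis if data from the last follow-up assessment is available" (Statistical Considerations). No dropout rate is given.

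**Assumptions, none stated in the document**
- 1:1 allocation, so 44 / 2 = 22 per arm.
- Complete follow-up.
- Two-sided 0.05.
- Effects in units of the SD of the change score.
- A single two-sample t-test on change. For a Wilcoxon test or the ANOVA the figures are a guide only.

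**Precision.** Half-width of the 95% interval = t(0.975, 42 df) × SD × √(2/22) = 2.018 × 0.3015 × SD ≈ 0.61 SD.

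**Chance of a non-significant result.** The noncentrality is d / √(2/22) = 3.317 d, where d is the true increase in SDs. The exact noncentral t distribution gives:

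| True increase | Noncentrality | Power | Missed |
|---|---|---|---|
| 0.5 SD | 1.658 | 0.367 | 63% |
| 0.6 SD | 1.990 | 0.494 | 51% |
| 0.8 SD | 2.653 | 0.736 | 26% |
| 1.0 SD | 3.317 | 0.900 | 10% |

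Power reaches 50% at 0.605 SD and 80% at 0.865 SD.

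**In pain points** (assumed SD of change from 1.5 to 3):

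| SD | 95% half-width | 1-point rise missed | 2-point rise missed |
|---|---|---|---|
| 1.5 | 0.91 | 42% | 1% |
| 2.0 | 1.22 | 63% | 10% |
| 2.5 | 1.52 | 75% | 26% |
| 3.0 | 1.83 | 81% | 42% |

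**Sensitivity of the proportion missed.** The 18 per arm and the Bonferroni divisors are illustrations; the document gives neither.

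| Setting | 0.5 SD | 0.8 SD | 1.0 SD |
|---|---|---|---|
| 22 per arm, 0.05 | 0.633 | 0.264 | 0.100 |
| 18 per arm, 0.05 | 0.692 | 0.355 | 0.170 |
| 22 per arm, 0.05/3 | 0.786 | 0.433 | 0.209 |
| 22 per arm, 0.05/7 | 0.865 | 0.560 | 0.314 |

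**What a formal no-worsening claim would need.** Take one-sided 0.025, 80% power and a true difference of zero. Then n per arm = 2 × (1.960 + 0.842)² / (margin in SD)². This gives 63 per arm for a margin of 0.5 SD, 25 for 0.8 SD and 16 for 1.0 SD. With 22 per arm, power is Φ(3.317 × margin − 1.960): 38%, 76% and 91% respectively. The margins are assumptions.

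**The case against.** Three stronger readings are tempting, and the text does not support them.

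1. **That the plan sets a safety hypothesis which a non-significant test would confirm.** Pain and spasticity are secondary outcome measures. The word hypothesize is kept for the Fugl-Meyer score, and the no-difference statement is an expectation that also covers odometer reading and walking speed. Nowhere does the document say that a non-significant p-value will be reported as absence of harm. A reader may fairly worry about this because no other criterion is offered, but it remains an inference.

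2. **That the trial would usually miss a real increase in pain.** That holds only below about 0.6 SD. A 2-point rise at an SD of 2 is missed 10% of the time, and a 1-point rise at an SD of 1.5 is missed 42% of the time. The document supplies no SD and no clinically important difference, so it cannot show which of these cases applies.

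3. **That Bonferroni makes the position much worse.** The correction is attached to follow-up tests after the ANOVA, and the sentence that names pain and Ashworth scores mentions none. Because the ANOVA is planned for every outcome, the text can be read either way, and it gives no number of comparisons. The corrected rows above are therefore illustrations.

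It is also fair to say that the ANOVA, particularly with a baseline covariate, could be more precise than a simple t-test. That would change the miss rates but not the logic, since it too tests for a difference. What stands after all this is that nothing in the plan could show that pain or tone did not rise.

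**Conclusion.** The point holds as one about inference and reporting for two secondary outcomes. The expectation for pain and spasticity can be met simply by failing to reject, and failing to reject is weak evidence at this sample size. On the assumptions listed, the interval reaches about 0.61 SD either side of the estimate, and increases of 0.5, 0.8 and 1.0 SD are missed about 63%, 26% and 10% of the time. Fewer analysed participants, or a correction if one applies, would raise those rates. Large increases would probably be detected; moderate ones often would not. The document does not support saying that the trial has committed itself to a claim of no harm. The primary Fugl-Meyer comparison is unaffected. This is a cheap improvement worth making before the data are analysed.

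**What to change.** In the Statistical Considerations section:

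- Replace the expectation of no significant difference, for pain and spasticity, with a commitment to report the between-arm difference in change from baseline at Evaluations 2 and 3, each with an unadjusted 95% confidence interval.
- State that a non-significant p-value for these outcomes will not be reported as absence of a difference.
- If a claim of no worsening is wanted, fix a margin with its justification before the data are seen, and base the claim on the upper confidence limit lying below it. Without a margin, the upper limit has nothing to be compared with.

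Two additions are optional. One is to say whether Bonferroni reaches these outcomes. The other is to tabulate the number per arm above the trial's own pain entry limit of 6, bearing in mind that this is an eligibility threshold and that such counts may say little with about 22 per arm.

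The cost is a few sentences and one table, using data already scheduled for collection. No extra participants are needed unless a formal non-inferiority claim with a tight margin is sought. The downside is that the trial may have to say that its data do not exclude a moderate increase in pain or tone.

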Appendix A

Part 1: Arm Strengthening Exercises with Tabletop Support

[figure not shown]
These exercises for the joints of the arm can help strengthen weak arm muscles, improve range of motion, and minimize stiffness and pain.

Instructions

- Use the muscles of your weak arm as much as possible.
- Use the stronger arm to help guide the weaker arm only as needed.
- Move slowly.
- The movements should not cause pain, but you may feel your muscles stretch.
- Repeat each exercise ten times.
- Perform exercises _____times per day.

Exercises

(1) Shoulder and Elbow Flexion/Extension

- 1. Place towel on the table
- 2. Place weaker arm on top of towel.
- 3. Using the strength of your shoulder and elbow, stretch your arm out in front of you
- 4. Try to keep arm as straight as possible.
- 5. Using the strength of your weaker arm, bend your elbow.
- 6. Pull arm back towards you.

(2) Shoulder Abduction/Adduction

- 1. Using the strength of your shoulder, slide arm out away from you.
- 2. Try to keep elbow straight and move only at the shoulder.
- 3. Slide arm in and around toward the opposite side of your body.
- 4. Try to keep elbow straight and move only at the shoulder.

(3) ShoulderInternal/ExternalRotation

- 1. Bend arm at elbow and tuck elbow in at your side.
- 2. Pull your arm in, toward your body.
- 3. Now slide hand out away from your body.
- 4. Keep elbow tucked in as much as possible. (You may need to use stronger hand to hold the weaker elbow in during this movement).

(4) Forearm Supination/Pronation

- 1. Place weaker elbow on the table.
- 2. Allow weaker forearm to rest in the palm of the stronger hand.
- 3. Using the strength of your weaker arm, turn palm toward you.
- 4. Keep hands in the same position.
- 5. Using the strength of your weaker arm, turn your palm away from you.

(5) Wrist Flexion/Extension

- 1. Hold weaker arm behind the wrist with your stronger hand, and lift the weaker arm slightly off the table. This will help your weaker hand to move without rubbing on the table.
- 2. Using the strength of your weaker arm, bend wrist forward.
- 3. Using the strength of your weaker arm, bend wrist backward.

(6) Finger and Thumb Flexion/Extension

- 1. Hold weaker arm behind the wrist with your stronger hand, and lift the weaker arm slightly off the table. This will help your weaker hand to move without rubbing on the table.
- 2. Using the strength of your weaker hand, close fingers into a fist.
- 3. Using the strength of your weaker hand, open all of your fingers and straighten thumb.

Part 2: Weight Bearing Exercises for the Arm

These exercises can help maintain range of movement and minimize stiffness and pain in the arm joints.

Instructions

- Move slowly and carefully. Stretches should not cause pain.
- Hold each position for at least 20 to 60 seconds.
- Perform exercises five times.
- If unable to stand easily, do only the first exercise

(1) SittingWeightBearing-Elbow/Wrist/FingerExtension

- 1. Place two stable chairs (of the same height) next to each other.
- 2. Place weaker hand on the seat next to you, as close to your body as possible.
- 3. Try to open weaker hand and place palm flat.
- 4. If unable to open hand, try placing only the heel of hand on the chair.
- 5. Use stronger hand to help straighten weaker elbow by placing hand behind elbow and pulling forward. Keep weaker arm as straight as possible.
- 6. Push down through the heel.
- 7. Hold position for 20-60 seconds.
- 8. To increase the stretch if desired, keep weaker hand on chair with elbow straight while stronger arm reaches forward and up.
- 9. Hold position for 20-60 seconds.

(2) StandingWeightBearing-Elbow/Wrist/FingerExtension

- 1. Stand facing a table. Place weaker hand on top of table, as close to your body as possible.
- 2. Try to open weaker hand and place palm flat.
- 3. If unable to open hand, try placing only the heel of hand on the table.
- 4. Use stronger hand to help straighten weaker elbow by placing hand behind elbow and pulling forward.
- 5. Keep weaker arm as straight as possible and push down through the heel of hand.
- 6. Hold position for 20-60 seconds.
- 7. To increase stretch if desired, keep weaker hand on chair and elbow straight while stronger arm reaches forward and up.
- 8. Hold position for 20-60 seconds.
